10.4. Appendix 4: Genetics

Use/Analysis of DNA

Genetic variation may impact a patient's response to IP, susceptibility to, and severity and progression of disease. Variable response to IP may be due to genetic determinants that impact drug absorption, distribution, metabolism, and excretion; mechanism of action of the drug; disease etiology; and/or molecular subtype of the disease being treated. Therefore, where local regulations and IRB/IEC allow, a blood sample will be collected for DNA analysis from patients consenting to provide the sample.

DNA samples will be used for research related to this trial may consist of the analysis of one or more candidate genes or the analysis of genetic markers throughout the genome (as appropriate).

The results of genetic analyses may be reported in the clinical study report or in a separate trial summary.

Cytokinetics will store the DNA samples in a secure storage space with adequate measures to protect confidentiality.

10.5. Appendix 5: Liver Safety: Actions and Follow-up Assessments

Drug-induced Liver Injury Reporting & Additional Assessments

To facilitate appropriate monitoring for signals of DILI, cases of concurrent aspartate aminotransferase (AST) or alanine aminotransferase (ALT) and total bilirubin (TBL) and/or international normalized ratio (INR) elevation require the following:

- The event is to be reported to Cytokinetics as an SAE within 24 hours of discovery or notification of the event (ie, before additional etiologic investigations have been concluded)
- The AE CRF that captures information necessary to facilitate the evaluation of treatment-emergent liver abnormalities is to be completed and sent to Cytokinetics.

Other events of hepatotoxicity and potential DILI are to be reported as SAEs if they meet the criteria for an SAE defined in [Section 8.4.1.2](#).

Criteria for Permanent Discontinuation of Investigational Product and Other Protocol-required Therapies due to Potential Hepatotoxicity

CK-3773274 **must** be discontinued permanently and the patient should be followed according to the following recommendations for possible DILI, if ALL of the criteria below are met:

- TBL $>2 \times$ ULN or INR >1.5

AND

- increased AST or ALT from the relevant baseline value as specified below:

Baseline AST or ALT Value	AST or ALT Elevation
<ULN	$>3 \times$ ULN

AND

- no other cause for the combination of the above laboratory abnormalities is apparent; important alternative causes for elevated AST/ALT and TBL values include, but are not limited to:
 - hepatobiliary tract disease
 - viral hepatitis (eg, Hepatitis A/B/C/D/E, Epstein-Barr Virus, cytomegalovirus, Herpes Simplex Virus, Varicella, toxoplasmosis, and Parvovirus)
 - right sided heart failure, hypotension, or any cause of hypoxia to the liver causing ischemia
 - exposure to hepatotoxic agents/drugs or hepatotoxins, including herbal and dietary supplements, plants and mushrooms
 - heritable disorders causing impaired glucuronidation (eg, Gilbert's Syndrome, Crigler-Najjar syndrome) and drugs that inhibit bilirubin glucuronidation (eg, indinavir, atazanavir)

- alpha-one antitrypsin deficiency
- alcoholic hepatitis
- autoimmune hepatitis
- Wilson’s disease and hemochromatosis
- nonalcoholic fatty liver disease including steatohepatitis
- nonhepatic causes (eg, rhabdomyolysis, hemolysis)

Criteria for Conditional Interruption of Investigational Product and Other Protocol-required Therapies due to Potential Hepatotoxicity

For patients who do not meet the criteria for permanent discontinuation of IP outlined above and have no underlying liver disease, the following rules are recommended for interruption of IP and other protocol required therapies:

- Elevation of either AST or ALT according to the following schedule:

Baseline AST or ALT Value	AST or ALT Elevation
Any	>8 × ULN at any time
Any	>5 × ULN but <8 × ULN for ≥2 weeks
Any	>5 × ULN but <8 × ULN and unable to adhere to enhanced monitoring schedule
Any	>3 × ULN with clinical signs or symptoms that are consistent with hepatitis (such as right upper quadrant pain/tenderness, fever, nausea, vomiting, jaundice)

OR

- TBL >3 × ULN at any time

IP and other protocol-required therapies, as appropriate must be withheld pending investigation into alternative causes of DILI. If IP is withheld, the patient is to be followed according to recommendations in this section for possible DILI. Rechallenge may be considered if an alternative cause for impaired liver tests (ALT, AST, ALP) and/or elevated TBL, is discovered and the laboratory abnormalities resolve to normal or baseline.

Rechallenge of Investigational Product and Other Protocol-required Therapies After Potential Hepatotoxicity

The decision to rechallenge the patient must be discussed and agreed upon unanimously by the patient, investigator, and Medical Monitor. Patients reinitiating IP after withholding for potential hepatotoxicity will restart IP, according to initial randomized allocation, on the same IP dose as established before the event and will not further titrate the dose.

If signs or symptoms recur with rechallenge, then IP must be permanently discontinued. Patients who clearly meet the criteria for permanent discontinuation must never be rechallenged.

Additional Clinical Assessments and Observation

All patients in whom IP(s) or protocol-required therapies is/are withheld (either permanently or conditionally) due to potential DILI or who experience AST or ALT elevations $>3 \times$ ULN are to undergo a repeat test and a period of “close observation” until abnormalities have stabilized, returned to normal, or returned to the patient’s baseline levels. Recommended assessments and testing frequency that are to be performed during this period include:

- Repeat AST, ALT, ALP, bilirubin (total and direct), and INR within 48 hours of receiving results with repeat testing until stabilized
- In cases of TBL $>2 \times$ ULN or INR >1.5 , retesting of liver tests, bilirubin (total and direct), and INR should be performed within 48 hours of receiving results with repeat testing 2-3 times per week until stabilized

Testing frequency of the above laboratory tests may decrease if the abnormalities stabilize or the IP(s) or protocol-required therapies has/have been discontinued AND the patient is asymptomatic.

- Initiate investigation of alternative causes for elevated AST or ALT and/or elevated TBL:
 - Obtain complete blood count (CBC) with differential to assess for eosinophilia
 - Obtain serum total immunoglobulin IgG, Anti-nuclear antibody (ANA), Anti Smooth Muscle Antibody, and Liver Kidney Microsomal antibody 1 (LKM1) to assess for autoimmune hepatitis
 - Obtain serum acetaminophen (paracetamol) levels
 - Obtain a more detailed history of:
 - Prior and/or concurrent diseases or illness
 - Exposure to environmental and/or industrial chemical agents
 - Symptoms (if applicable) including right upper quadrant pain, hypersensitivity type reactions, fatigue, nausea, vomiting and fever
 - Prior and/or concurrent use of alcohol, recreational drugs and special diets
 - Concomitant use of medications (including non-prescription medicines and herbal and dietary supplements), plants, and mushrooms
 - Obtain viral serologies
 - Obtain creatine phosphokinase, haptoglobin, lactate dehydrogenase, and peripheral blood smear
 - Perform appropriate liver imaging if clinically indicated
- Obtain appropriate blood sampling for PK analysis if this has not already been collected
- Obtain hepatology consult (liver biopsy may be considered in consultation with an hepatologist)

Follow the patient and the laboratory tests (ALT, AST, TBL, INR) until all laboratory abnormalities return to baseline or normal. The “close observation period” is to continue for a minimum of 4 weeks after discontinuation of all IP(s) and protocol required therapies.

The potential DILI event and additional information such as medical history, concomitant medications, and laboratory results must be captured in corresponding CRFs.

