215. Hepatic impairment defined by a total bilirubin (TBL) $\geq 1.5 \times$ the upper limit of normal (ULN), or alanine aminotransferase (ALT) or aspartate aminotransferase (AST) $\geq 3 \times$ ULN at screening. Patients with documented Gilbert syndrome and TBL $\geq 1.5 \times$ ULN due to unconjugated hyperbilirubinemia, without other hepatic impairment, are permitted.
216. Recipient of a major organ transplant (eg, heart, lung, liver, bone marrow, renal) or anticipated transplantation within 12 months from randomization.
217. History or evidence of any other clinically significant disorder, malignancy, active infection, other condition, or disease that, in the opinion of the investigator or the Medical Monitor, would pose a risk to patient safety or interfere with the trial evaluation, procedures, or completion.

218. Estimated glomerular filtration rate (eGFR) <30 mL/min/1.73 m² (by the modified Modification of Diet in Renal Disease equation) at screening.
219. Currently participating in another investigational device or drug trial or received an investigational device or drug <1 month (or 5 half-lives for drugs, whichever is longer) prior to screening. Other investigational procedures while participating in this trial are not permitted.

Note: At the EOS visit for CY 6031, screening assessments for entry into an open-label extension study of aficamten are permitted.
220. Has received prior treatment with CK-3773274 or mavacamten.
221. Any known hypersensitivity to excipients in study drug tablets

Exclusion Criteria for CMR sub-study

222. Inability to tolerate CMR.
223. Has an ICD.
224. Has a cardiac pacemaker.
225. Does not consent to participate in CMR sub-study

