6.7. Access to Investigational Product after the End of the Study

Patients who complete CY 6031 and meet eligibility criteria will be offered participation in an open-label extension study of aficamten. Participation in the open-label extension study is at the discretion of the patient and not a condition of participation in CY 6031. The commitment to the conduct of an open-label extension trial will be at Cytokinetics's discretion.

7. TEMPORARY INTERRUPTION OF INVESTIGATIONAL PRODUCT, DISCONTINUATION OF INVESTIGATIONAL PRODUCT, AND PATIENT CONSENT WITHDRAWAL

Emergent safety concerns should be discussed with the Medical Monitor immediately upon occurrence or awareness to determine if the patient should continue, interrupt or permanently discontinue IP.

Unless a safety concern arises, the investigator should make every effort to keep a patient on the IP for as long as possible during the trial. The degree to which a patient withdraws from the trial varies. There are three types of discontinuation: temporary IP interruption, permanent IP discontinuation and patient withdrawal of consent.

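### The mandatory liver stop in Appendix 5 has no AST/ALT threshold for patients who enter with both enzymes at or above the upper limit of normal

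*Protocol*

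**What the plan says.** Protocol Section 10.5 (Appendix 5) sets a mandatory permanent stop when all of three limbs are met:

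1. TBL >2 x ULN or INR >1.5.
2. "increased AST or ALT from the relevant baseline value as specified below". The table has a single row: baseline <ULN, elevation >3 x ULN.
3. No other apparent cause for the combination of abnormalities.

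On rechallenge it adds: "Patients who clearly meet the criteria for permanent discontinuation must never be rechallenged". Section 7.2 lists meeting all these criteria as a reason for permanent discontinuation.

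A second set of rules covers interruption. It is for patients who do not meet the permanent criteria and who "have no underlying liver disease, the following rules are recommended for interruption of IP and other protocol required therapies". The baseline entry is *Any* in all four AST/ALT rows:

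- >8 x ULN;
- >5 to <8 x ULN for at least 2 weeks;
- >5 to <8 x ULN when enhanced monitoring cannot be followed;
- >3 x ULN with signs or symptoms of hepatitis.

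TBL >3 x ULN is a further trigger. INR is not a trigger. Once one is met, product "must be withheld pending investigation into alternative causes of DILI". "Rechallenge may be considered if an alternative cause for impaired liver tests" or raised bilirubin is found and the tests resolve.

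Exclusion criterion 215 (Section 5.2) bars AST or ALT of 3 x ULN or more at screening, and nothing lower.

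**The concern.** Eligibility and the stopping rule do not match. Patients may enter with AST and ALT anywhere from ULN to just under 3 x ULN, but the stopping table gives no threshold for such a baseline. Because the limbs are joined by AND, an undefined second limb disables the whole rule.

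A patient with only one raised enzyme can still qualify through the other. A patient with both raised cannot qualify at all, whatever happens on treatment, and the absolute bar on rechallenge falls with the stop.

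At stake is consistency in a safety rule. Two patients with identical on-treatment results and no other cause could be handled differently, one by a mandatory stop and one by judgement, solely because of a baseline the protocol permits.

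**Working it through.** The plan gives no figure to reproduce, so the check applies the Appendix 5 criteria literally. All enzyme and TBL values are in multiples of ULN.

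**Two worked cases.** On-treatment AST and ALT are both 4.5. There is no other cause, no underlying liver disease, and no sign or symptom of hepatitis (so no visible jaundice).

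| | Case A | Case B |
|---|---|---|
| TBL; INR | 2.5; normal | 0.8; 1.8 |
| Limb 1 (TBL >2 or INR >1.5) | met | met |
| Limb 2, both baselines 0.9 | met (4.5 >3) | met (4.5 >3) |
| Limb 2, both baselines 1.5 | no row, not met | no row, not met |
| Permanent stop, baselines 0.9 | mandatory | mandatory |
| Permanent stop, baselines 1.5 | not triggered | not triggered |
| Interruption: enzymes >5 | no | no |
| Interruption: >3 with signs or symptoms | no | no |
| Interruption: TBL >3 | no | no |

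With baselines of 1.5, neither case triggers either rule.

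**Grid.** Baseline AST and ALT each take 0.5, 0.9, 1.0, 1.5, 2.0, 2.9. On-treatment AST and ALT each take 2.0, 3.5, 4.5, 5.5, 7.5, 9.0. TBL takes 0.8, 2.5, 3.5 and INR takes 1.0, 1.8. Cells are kept if (TBL >2 or INR >1.5) and at least one enzyme is >3.

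- Enzyme pairs with at least one >3: 6 x 6 − 1 = 35.
- TBL/INR pairs meeting limb 1: 3 x 2 − 1 = 5.
- Profiles per baseline pair: 35 x 5 = 175.
- Both baselines raised: 4 x 4 = 16 pairs, 16 x 175 = 2,800 cells.
- Both baselines below ULN: 2 x 2 = 4 pairs, 4 x 175 = 700 cells.

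*Mandatory stop:* 700 of 700 with both baselines below ULN; 0 of 2,800 with both raised.

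*Interruption, both raised, asymptomatic, monitoring kept, rise >5 lasting under 2 weeks:*

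- TBL 3.5 triggers in 2 of the 5 TBL/INR pairs: 2 x 35 = 70 profiles.
- In the other 3 pairs, an enzyme >8 triggers: 36 − 25 = 11 enzyme pairs, 3 x 11 = 33 profiles.
- Total (70 + 33) x 16 = 1,648. Neither rule: 2,800 − 1,648 = 1,152.

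*If enzymes >5 persist for 2 weeks or more:*

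- Uncovered enzyme pairs have both values at or below 5 and at least one >3: 3 x 3 − 1 = 8.
- Neither rule: 8 x 3 x 16 = 384, and 384 / 2,800 = 13.7%. Covered by interruption: 2,416.
- The 384 split equally, 128 each, across (TBL 2.5, INR 1.0), (TBL 2.5, INR 1.8) and (TBL 0.8, INR 1.8).

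The uncovered band is therefore enzymes >3 to 5 for any duration, or >5 to <8 for under 2 weeks with monitoring kept, together with either TBL >2 to 3, or INR >1.5 with TBL at or below 3. A value of exactly 8 also falls between the interruption rows.

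**Patients exposed.** The documents do not say how many will have both enzymes raised at baseline. Assuming 1% to 10% of the roughly 135 active patients (Section 9.2): 135 x 0.01 = 1.35 and 135 x 0.10 = 13.5, so about 1 to 14 would lie outside the rule. Those who also have such an event would be far fewer.

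**The case against.** - **Most of the risk is handled elsewhere.** Concurrent enzyme and TBL/INR elevation is an SAE reportable within 24 hours. Section 7 says: "Emergent safety concerns should be discussed with the Medical Monitor immediately upon occurrence or awareness". Tests are repeated within 48 hours and, once TBL is >2 x ULN or INR >1.5, there is "repeat testing 2-3 times per week until stabilized", so later triggers would be seen. A hepatology consult is listed, and the investigator or sponsor may stop treatment. Rechallenge needs unanimous agreement, and recurrence on rechallenge is a mandatory stop at any baseline. All of this stands. It shows that monitoring is adequate, but for a first event in the band every route to stopping is discretionary.
- **Section 6.6.4 ties the criteria to an external regulatory guidance.** That source is not in the documents, so the finding is limited to the protocol as written. Section 6.6.4 itself gives no thresholds and sends sites to Appendix 5.
- **Jaundice is an interruption sign.** At TBL 2.5 x ULN, visible jaundice would trigger withholding. That narrows the two TBL 2.5 groups (256 of the 384 cells) but leaves the INR-only group untouched.
- **INR is normally measured only at screening and at unscheduled liver-injury visits, and anticoagulated patients are admitted.** So the INR band arises inside a work-up, and a wider rule could catch an anticoagulant effect. The no-other-cause limb can deal with that, since its list is not exhaustive. The same exposure already exists for patients with normal baselines.
- **The threshold for a raised baseline is a clinical choice.** True. The documents give neither a threshold nor a reason for leaving these patients to judgement.
- **A table row may have been lost in PDF reading.** This cannot be fully excluded, but the adjacent four-row table came through intact and nothing marks a redaction.

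**Conclusion.** The gap is real on the text. For an eligible patient with both AST and ALT at or above ULN at baseline, the laboratory-based mandatory stop and its rechallenge bar can never apply. The interruption rules cover the more severe cases and leave the band described above to judgement.

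The grid percentages depend on the chosen values and are not patient frequencies; the firm results are the zero for the mandatory stop and the existence of the band. The check assumes no underlying liver disease. A patient who has it is outside the interruption rules as written, so for that patient the uncovered range is wider.

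The issue is minor: what is missing is a fixed stop, not surveillance; few patients are likely to be affected; and no endpoint or efficacy analysis changes.

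**What to change.** In the permanent-discontinuation table, change the baseline entry from <ULN to *Any*. Keep >3 x ULN, the TBL/INR limb and the no-other-cause limb as they are. Section 7.2 and the rechallenge bar then follow without further edits. If the sponsor prefers a different threshold for raised baselines, a second row for baseline at or above ULN would also close the gap.

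The cost is one table entry in an amendment or clarification letter, with no added tests or visits. The downside is a smaller rise needed to meet the enzyme limb from a high baseline: 3 / 2.9 is about 3%, against 100% from 1.5 x ULN (3 / 1.5) and 233% from 0.9 x ULN (3 / 0.9). The other two limbs must still be met, which limits over-triggering.

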10.6. Appendix 6: Abbreviations

Table 10: List of Abbreviations

Abbreviation/Term	Explanation
AE	Adverse event
ALP	Alkaline phosphatase
ALT	Alanine aminotransferase
ANA	Anti-nuclear antibody
AST	Aspartate aminotransferase
CBC	Complete blood count
CGI	Clinical Global Impression scale
CI	Confidence interval
CIOMS	Council for International Organizations of Medical Sciences
C _{max}	Maximum plasma concentration observed
C _{trough}	Trough plasma concentration observed
CMH	Cochran–Mantel–Haenszel
CMR	Cardiac magnetic resonance
CPET	Cardiopulmonary exercise testing
CRF	Case report form
CRO	Contract research organization
CV	Cardiovascular
CYP	Cytochrome P450
DILI	Drug induced liver injury
DMC	Data monitoring committee
EC	Executive Committee
ECG	Electrocardiogra(m/phy)
ED	Early discontinuation
EOS	End of study
EOT	End of treatment
EQ-5D-5L	EuroQol 5-dimension 5-level instrument
FAS	Full analysis set
FSH	Follicle-stimulating hormone
FU	Follow up
GCP	Good Clinical Practice

Abbreviation/Term	Explanation
GLP	Good Laboratory Practice
HCM	Hypertrophic cardiomyopathy
HIPAA	Health Insurance Portability and Accountability Act
hs-cTnI	High sensitivity cardiac troponin I
IB	Investigator's Brochure
ICD	Implantable cardioverter defibrillators
ICF	Informed consent form
ICH	International Council for Harmonisation
IEC	Independent ethics committee
IgG	Immunoglobulin G
IMP	Investigational medicinal product
INR	International normalized ratio
IP	Investigational product
IRB	Institutional review board
IUD	Intrauterine device
IUS	Intrauterine hormone-releasing system
IWRS	Interactive web response system
KCCQ	Kansas City Cardiomyopathy Questionnaire
LAM	Lactational amenorrhoea method
LKM1	Liver Kidney Microsomal antibody 1
LSM	Least squares mean
LV	Left ventricle(ular)
LVEDV	Left ventricular end-diastolic volume
LVEF	Left ventricular ejection fraction
LVESV	Left ventricular end-systolic volume
LVFS	Left ventricular fractional shortening
LVOT	Left ventricular outflow tract
LVOT-G	Left ventricular outflow tract gradient
MedDRA	Medical Dictionary for Regulatory Activities
NIMP	Non-investigational medicinal product
NT-proBNP	n-terminal prohormone brain natriuretic peptide
NYHA	New York Heart Association

Abbreviation/Term	Explanation
oHCM	Obstructive hypertrophic cardiomyopathy
PD	Pharmacodynamics
PDS	Pharmacodynamics analysis set
PGI-C	Patient Global Impression of Change scale
PK	Pharmacokinetics
PKS	Pharmacokinetics analysis set
PRO	Patient-reported outcomes
pVO ₂	Peak oxygen uptake
RBC	Red blood cell
RER	Respiratory exchange ratio
SAE	Serious adverse event
SAS	Safety analysis set
SAQ-7	Seattle Angina Questionnaire -7
SC	Steering Committee
SD	Standard deviation
SoA	Schedule of activities
SoC	Standard of care
TBL	Total bilirubin
ULN	Upper limit of normal
VAT	Ventilatory anaerobic threshold
WOCBP	Women of childbearing potential

10.7. Appendix 7: Protocol Amendment History

The Protocol Amendment Summary of Changes ([Table 1](#)) for the current amendment is located directly before the Table of Contents (TOC).

Investigators: Study Center(s): Patients will be enrolled from approximately 105 sites worldwide.												
Studied period (years): 2022 to 2023	Phase of development: Phase 3											
Objectives and Endpoints:												

  
 Objectives	Endpoint(s)	
   
 Primary	
 
  
 • To evaluate the effect of CK-3773274 on exercise capacity in patients with symptomatic oHCM 	 
 • Change in peak oxygen uptake (pVO₂) by cardiopulmonary exercise testing (CPET) from baseline to Week 24 	
 
 Secondary	
 
  
 • To evaluate the effect of CK-3773274 on patient health status • To evaluate the effect of CK-3773274 on New York Heart Association (NYHA) Functional Classification • To evaluate the effect of CK-3773274 on post-Valsalva left ventricular outflow tract gradients (LVOT-G) • To evaluate the effect of CK-3773274 on duration of eligibility for septal reduction therapy • To evaluate the effect of CK-3773274 on exercise capacity 	 
 • Change in Kansas City Cardiomyopathy Questionnaire – Clinical Summary Score (KCCQ-CSS) from baseline to Week 12 and Week 24 • Proportion of patients with ≥1 class improvement in NYHA Functional Class from baseline to Week 12 and Week 24 • Change in post-Valsalva LVOT-G from baseline to Week 12 and Week 24 • Proportion of patients with post-Valsalva LVOT-G <30 mmHg at Week 12 and Week 24 • Total duration of septal reduction therapy (SRT) eligible during the 24 Week treatment period in patients who were SRT eligible at baseline • Change in total workload during CPET from baseline to Week 24 	
  
			Objectives	Endpoint(s)	Primary		
 • To evaluate the effect of CK-3773274 on exercise capacity in patients with symptomatic oHCM 	
 • Change in peak oxygen uptake (pVO₂) by cardiopulmonary exercise testing (CPET) from baseline to Week 24 	Secondary		
 • To evaluate the effect of CK-3773274 on patient health status • To evaluate the effect of CK-3773274 on New York Heart Association (NYHA) Functional Classification • To evaluate the effect of CK-3773274 on post-Valsalva left ventricular outflow tract gradients (LVOT-G) • To evaluate the effect of CK-3773274 on duration of eligibility for septal reduction therapy • To evaluate the effect of CK-3773274 on exercise capacity 	
 • Change in Kansas City Cardiomyopathy Questionnaire – Clinical Summary Score (KCCQ-CSS) from baseline to Week 12 and Week 24 • Proportion of patients with ≥1 class improvement in NYHA Functional Class from baseline to Week 12 and Week 24 • Change in post-Valsalva LVOT-G from baseline to Week 12 and Week 24 • Proportion of patients with post-Valsalva LVOT-G <30 mmHg at Week 12 and Week 24 • Total duration of septal reduction therapy (SRT) eligible during the 24 Week treatment period in patients who were SRT eligible at baseline • Change in total workload during CPET from baseline to Week 24
Objectives	Endpoint(s)											
Primary												

 • To evaluate the effect of CK-3773274 on exercise capacity in patients with symptomatic oHCM 	
 • Change in peak oxygen uptake (pVO₂) by cardiopulmonary exercise testing (CPET) from baseline to Week 24 											
Secondary												

 • To evaluate the effect of CK-3773274 on patient health status • To evaluate the effect of CK-3773274 on New York Heart Association (NYHA) Functional Classification • To evaluate the effect of CK-3773274 on post-Valsalva left ventricular outflow tract gradients (LVOT-G) • To evaluate the effect of CK-3773274 on duration of eligibility for septal reduction therapy • To evaluate the effect of CK-3773274 on exercise capacity 	
 • Change in Kansas City Cardiomyopathy Questionnaire – Clinical Summary Score (KCCQ-CSS) from baseline to Week 12 and Week 24 • Proportion of patients with ≥1 class improvement in NYHA Functional Class from baseline to Week 12 and Week 24 • Change in post-Valsalva LVOT-G from baseline to Week 12 and Week 24 • Proportion of patients with post-Valsalva LVOT-G <30 mmHg at Week 12 and Week 24 • Total duration of septal reduction therapy (SRT) eligible during the 24 Week treatment period in patients who were SRT eligible at baseline • Change in total workload during CPET from baseline to Week 24 											

Methodology:

This is a Phase 3 randomized, placebo-controlled, double-blind, multi-center trial in patients with symptomatic oHCM. Approximately 270 eligible patients will be randomized in a 1:1 ratio to receive CK-3773274 or placebo. Doses of 5, 10, 15, or 20 mg or matching placebo will be administered in an escalating manner using echocardiography to guide dose titration. Randomization will be stratified by use of beta-blockers and CPET exercise modality.

The trial will comprise three periods. The screening period will be up to 6 weeks in duration. The double-blind placebo-controlled treatment period will last 24 weeks. Following the final dose of investigational product (IP), there will be a 4-week safety follow-up period. IP will be administered orally once daily. During the initial six weeks of the treatment period, IP doses will be individually titrated at Weeks 2, 4, and 6 using echocardiography. Dose escalation at the Weeks 2, 4, and 6 visits will occur only if a patient has a post-Valsalva LVOT-G ≥ 30 mmHg and a biplane LVEF $\geq 55\%$. An echocardiogram will be performed at each subsequent visit during the trial and the dose down-titrated if necessary. The primary endpoint of pVO₂ will be measured by CPET at screening and at end of treatment (Week 24).

Number of Subjects (planned and analyzed): Approximately 270 patients will be randomized to CK-3773274 or placebo at 1:1 ratio.

Diagnosis and main criteria for inclusion:

The key inclusion criteria are below. A full listing of eligibility criteria can be found in protocol Section 5.

- Males and females between 18 and 85 years of age, inclusive, at screening.
- Body mass index < 35 kg/m².
- Diagnosed with HCM per the following criteria:
 - Has LV hypertrophy and non-dilated LV chamber in the absence of other cardiac disease and
 - Has an end-diastolic LV wall thickness as measured by the echocardiography core laboratory of:
 - ≥ 15 mm in one or more myocardial segments OR
 - ≥ 13 mm in one or more wall segments and a known-disease-causing gene mutation or positive family history of HCM
- Has resting LVOT-G ≥ 30 mmHg and post-Valsalva LVOT-G ≥ 50 mmHg during screening as determined by the echocardiography core laboratory.
- LVEF $\geq 60\%$ at screening as determined by the echocardiography core laboratory.
- NYHA Functional Class II or III at screening.
- Hemoglobin ≥ 10 g/dL at screening.
- Respiratory exchange ratio (RER) ≥ 1.05 and pVO₂ $\leq 90\%$ predicted on the screening CPET per the core laboratory.
- Patients on beta-blockers, verapamil, diltiazem, or disopyramide should have been on stable doses for > 6 weeks prior to randomization and anticipate remaining on the same medication regimen during the trial. Patients treated with disopyramide must also be concomitantly treated with a beta blocker and/or calcium channel blocker

Test product, dose and mode of administration:

Aficamten will be administered orally once daily with or without food. Patients receiving CK-3773274 start at a dose of 5 mg once daily and may escalate through doses of 10, 15, and 20 mg once daily during the initial six weeks of treatment if they continue to meet the escalation criteria (post-Valsalva LVOT-G ≥ 30 mmHg and a biplane LVEF $\geq 55\%$) or will stop at their current dose when escalation criteria are not met.

Duration of treatment:

After signing the informed consent form, patients will complete assessments to determine trial eligibility during a screening period of up to 6 weeks in duration. The double-blind placebo-controlled treatment period will last 24 weeks. Following the final dose of IP, there will be a 4-week safety follow-up period.

Reference therapy, dose and mode of administration:

Doses of 5, 10, 15, or 20 mg or matching placebo will be administered in an escalating manner using echocardiography to guide dose titration.

Criteria for evaluation (see protocol Section 3):

Efficacy:

The primary efficacy endpoint is change in peak oxygen uptake (pVO_2) by cardiopulmonary exercise testing (CPET) from baseline to Week 24.

The secondary endpoints are as follows:

- Change in Kansas City Cardiomyopathy Questionnaire – Clinical Summary Score (KCCQ-CSS) from baseline to Week 12 and Week 24
- Proportion of patients with ≥ 1 class improvement in NYHA Functional Class from baseline to Week 12 and Week 24
- Change in post-Valsalva LVOT-G from baseline to Week 12 and Week 24
- Proportion of patients with post-Valsalva LVOT-G < 30 mmHg at Weeks 12 and 24
- Change in total workload during CPET from baseline to Week 24
- Total duration of SRT eligible during the 24 Week treatment period in patients who were SRT eligible at baseline

Safety:

- Incidence of reported major adverse cardiac events (cardiovascular [CV] death, cardiac arrest, non-fatal stroke, non-fatal myocardial infarction, CV hospitalization)
- Incidence of new onset persistent atrial fibrillation
- Incidence of appropriate implantable cardiac defibrillator (ICD) discharges and aborted sudden cardiac death
- Incidence of left ventricular ejection fraction (LVEF) $< 50\%$
- Incidence of treatment emergent adverse events

Statistical methods:

Unless specified otherwise, efficacy analyses will be performed on the full analysis set (FAS), which includes all randomized patients. The primary analysis will test the null hypothesis that there is no treatment difference in the primary endpoint between patients randomized to placebo and those randomized to CK-3773274 in the FAS. Change from baseline in pVO₂ will be analyzed using an ANCOVA model with treatment group, randomization stratification factors, baseline pVO₂ and baseline weight as covariates.

For preservation of the overall type I error rate at two-sided 0.05 for the primary and secondary endpoints, the primary and secondary endpoints will be tested in the following specified order using a closed testing procedure. The primary endpoint is tested first at two-sided 0.05. If the primary endpoint achieves statistical significance at two-sided $p < 0.05$, then the secondary endpoints will be tested at two-sided 0.05, with their testing being in the sequential order of KCCQ-CSS change from baseline, proportion of patients with ≥ 1 NYHA functional class improvement, post-Valsalva LVOT-G change from baseline, and proportion of patients with post-Valsalva LVOT-G < 30 mmHg; duration of SRT eligibility for participants who are SRT eligible at baseline, for each after 24 weeks of treatment; then KCCQ-CSS change from baseline, proportion of patients with ≥ 1 NYHA functional class improvement, post-Valsalva LVOT-G change from baseline, and proportion of patients with post-Valsalva LVOT-G < 30 mmHg, for each after 12 weeks of treatment; and lastly change from baseline to Week 24 in total workload. SRT eligibility is defined as resting or post-Valsalva LVOT-G ≥ 50 mmHg AND NYHA Functional Class ≥ 3 . See below table for illustration of the testing order.

Primary Endpoint		Significance Level
Step 1	pVO ₂	0.05
Secondary Endpoints		↓
Step 2	KCCQ-CSS (24 wk)	0.05
		↓
Step 3	NYHA Class (24 wk)	0.05
		↓
Step 4	Valsalva Gradient (24 wk)	0.05
		↓
Step 5	%Valsalva Gradient (24 wk)	0.05
		↓
Step 6	Duration SRT Eligible (24 wk)	0.05
		↓
Step 7	KCCQ-CSS (12 wk)	0.05
		↓
Step 8	NYHA Class (12 wk)	0.05
		↓
Step 9	Valsalva Gradient (12 wk)	0.05
		↓
Step 10	%Valsalva Gradient (12 wk)	0.05
		↓
Step 11	Total workload (24 wk)	0.05

Multiplicity will be detailed in [Section 7.6](#).

The proportion of responders in various exploratory endpoints in FAS will be analyzed using Cochran–Mantel–Haenszel (CMH) test stratified by randomization factors. The p-value and 95% confidence interval (CI) will be obtained using exact method. Other change from baseline endpoints will be

analyzed using mixed measures repeated model with treatment, visit, randomization stratification factors, treatment by visit, baseline by visit interaction as fixed effect and baseline assessment as covariate. Total of SRT eligible will be analyzed using an ANCOVA model with treatment group and randomization stratification factor beta blocker use/no use as fixed effects adjusting for significant baseline characteristics.

Safety analyses will be performed on the safety analysis set (SAS) which includes all patients who received at least one dose of IP. The pharmacokinetics analysis set (PKS) will consist of patients who have at least one evaluable plasma concentration of CK-3773274.

The number and percentage of patients reporting any treatment-emergent AEs will be coded using the MedDRA dictionary and be tabulated by system organ class and preferred term.

TABLE OF CONTENTS

SIGNATURE PAGE	2
TECHNICAL SUMMARY REPORT (TSR).....	3
TABLE OF CONTENTS.....	8
LIST OF TABLES.....	11
LIST OF ABBREVIATIONS.....	12
SAP VERSION HISTORY	14
1. INTRODUCTION	16
2. STUDY OBJECTIVES AND ENDPOINTS.....	17
2.1. Study Objectives.....	17
2.1.1. Primary Objective.....	17
2.1.2. Secondary Objective.....	17
2.2. Study Endpoints.....	17
2.2.1. Primary Endpoints	17
2.2.2. Secondary Endpoints	17
2.2.3. Exploratory Endpoints.....	17
2.2.4. Safety Endpoints.....	19
2.2.5. PK Parameters	20
3. STUDY DESIGN	21
3.1. Summary of Study Design.....	21
3.2. Definition of Study Drugs	21
3.3. Sample Size Considerations	22
3.3.1. Sample Size Justifications	22
3.4. Randomization.....	22
3.5. Clinical Assessments	22
3.5.1. Efficacy Assessments	22
3.5.1.1. Echocardiography.....	22
3.5.1.2. Patient-Reported Outcomes.....	24
3.5.1.3. CMR Assessments.....	25
3.5.1.4. CPET Assessments.....	27
3.5.2. Safety Assessments.....	27
3.5.3. Pharmacokinetics Assessments	27

4.	PLANNED ANALYSES.....	28
4.1.	Interim Analyses.....	28
4.2.	Final Analyses.....	28
5.	GENERAL CONSIDERATIONS FOR DATA ANALYSES AND HANDLING.....	29
5.1.	General Summary Table and Individual Subject Data Listing Considerations.....	29
5.2.	General Post Text Summary Table and Individual Subject Data Listing Format Considerations.....	29
